**Table 5-2: Grading for Hand-Foot-Skin-Reaction**

	Grade 1	Grade 2	Grade 3
NCI-CTCAE v4.0 Palmar-plantar erythrodysesthesia syndromea	Minimal skin changes or dermatitis (e.g., erythema, edema, or hyperkeratosis) without pain	Skin changes (e.g., peeling, blisters bleeding, edema, or hyperkeratosis) with pain	Severe skin changes (e.g., peeling, blisters, bleeding, edema, or hyperkeratosis) with pain
Further description / examples of skin changes	Numbness, dysesthesia / paresthesia tingling, painless swelling, or erythema of the hands and/or feet	Painful erythema and swelling of the hands and/or feet	Moist desquamation, ulceration, blistering, or severe pain of the hands and/or feet
Effect on activities	Does not disrupt normal activities	Limiting instrumental activities of daily life (e.g., preparing meals, shopping for groceries or clothes, using the telephone, managing money)	Limiting self-care activities of daily life (e.g., bathing, dressing and undressing, feeding self, using the toilet, taking medications) and not bedridden

a. Palmer-plantar erythrodysesthesia syndrome is a disorder characterized by redness, marked discomfort, swelling, and tingling in the palms of hands or the soles of the feet.

**Table 5.3 Recommended dose modification for hand-foot-skin reactiona**

Grade of event (NCI-CTCAE v4.0)	Occurrence	Suggested Dose Modification
Grade 1	Any	Maintain dose level and immediately institute supportive measures for symptomatic relief
Grade 2	1 st occurrence	Consider decreasing dose by one dose level and immediately institute supportive measures. If no improvement, interrupt therapy for a minimum of 7 days, until toxicity resolves to Grade 0-1 b,c
	No improvement within 7 days or 2 nd occurrence	Interrupt therapy until toxicity resolves to Grade 0-1. c When resuming treatment, treat at reduced dose level. b
	3 rd occurrence	Interrupt therapy until toxicity resolves to Grade 0-1. c When resuming treatment, decrease dose by one dose level. b,d
	4 th occurrence	Discontinue therapy

Grade 3	1 st occurrence	Institute supportive measures immediately. Interrupt therapy for a minimum of 7 days until toxicity resolves to Grade 0-1. c When resuming treatment, decrease dose by one dose level. b,d
	2 nd occurrence	Institute supportive measures immediately. Interrupt therapy for a minimum of 7 days until toxicity resolves to Grade 0-1. c When resuming treatment, decrease dose by one additional dose level b,d
	3 rd occurrence	Discontinue treatment permanently.

a. More conservative management is allowed if judged medically appropriate by the investigator.  
 b. If toxicity returns to Grade 0-1 after dose reduction, dose re-escalation is permitted at the discretion of the investigator if subject has completed one cycle at reduced dose without recurrence of event.  
 c. If there is no recovery after a 4-week delay, treatment with regorafenib will be discontinued permanently.  
 d. Subjects requiring > 2 dose reductions should go off protocol therapy.  
 The maximum daily dose is 160 mg.

Prior to starting regorafenib and at first occurrence of HFSR, independent of grade, prompt institutional supportive measures such as topical emollients, low potency steroids, or non-urea-containing creams should be administered. Patients should be educated on prevention/management strategies for HFSR.

Recommended prevention/management strategies for skin toxicities consistent with HFSR are summarized below:

#### Control of calluses

Before initiating treatment with regorafenib:

- Check condition of hands and feet.
- Suggest a manicure/pedicure, when indicated.
- Recommend pumice stone use for callus or 'rough spot' removal.

During regorafenib treatment

- Avoid pressure points.
- Avoid items that rub, pinch or create friction.

#### Use of creams

- Non-urea based creams may be applied liberally.
- Keratolytic creams (e.g. urea-based creams, salicylic acid 6%) may be used sparingly and only to affected (hyperkeratotic) areas.
- Alpha hydroxyl acids (AHA) based creams may be applied liberally 2 times a day. Approximately 5% to 8% provides gentle chemical exfoliation.
- Topical analgesics (e.g. lidocaine 2%) are to be considered for pain control.

- Topical corticosteroids like clobetasol 0.05% should be considered for subjects with Grade 2 or 3 HFSR. Avoid systemic steroids.

Tender areas should be protected as follows

- Use socks/gloves to cover moisturizing creams
- Wear well-padded footwear
- Use insole cushions or inserts (e.g. silicon, gel)
- Foot soaks with tepid water and Epson salts

## 5.1 Hypertension

Hypertension is a known AE associated with regorafenib treatment. Subject will have their blood pressure measured at least weekly at the study site during the first 8 weeks of treatment. If additional blood pressure measurements are done outside the study site, and the blood pressure is  $\geq 140$  mmHg systolic or  $\geq 90$  mmHg diastolic then the subject must contact study personnel. The management of hypertension, including the choice of antihypertensive medication, will be performed according to local standards and to the usual practice of the investigator. Every effort should be made to control blood pressure by medical means other than study drug dose modification. If necessary, Table 5.4 outlines suggested dose reductions.

**Table 5-4: Management of Treatment-Emergent Hypertension**

Grade (CTCAE v4.0)	Antihypertensive Therapy	Regorafenib Dosing
1  Prehypertension (systolic BP 120 - 139 mmHg or diastolic BP 80 - 89 mmHg)	None	Continue regorafenib Consider increasing blood pressure (BP) monitoring
2  Systolic BP 140 - 159 mmHg or diastolic BP 90 - 99 mmHg  OR  Symptomatic increase by $> 20$ mmHg (diastolic) if previously within normal limits	Treat with the aim to achieve diastolic BP $\leq 90$ mmHg:  If BP previously within normal limits, start anti-hypertensive monotherapy  If patient already on anti-hypertensive medication, titrate up the dose.	Continue regorafenib  If symptomatic, hold regorafenib until symptoms resolve AND diastolic BP $\leq 90$ mmHg a . When regorafenib is restarted, continue at the same dose level.

3
 
Systolic BP <math>\geq</math> 160 mmHg or diastolic BP <math>\geq</math> 100 mmHg
 
OR
 
More than one drug or more intensive therapy than previously used indicated
	
Treat with the aim to achieve diastolic BP <math>\leq</math> 90 mmHg:
 
Start anti-hypertensive medication
 
AND/OR
 
Increase current anti-hypertensive medication
 
AND/OR
 
Add additional anti-hypertensive medications.
	
Hold regorafenib until diastolic BP <math>\leq</math> 90 mmHg and, if symptomatic, until symptoms resolve.a
 
When regorafenib is restarted, continue at the same dose level.
 
If BP is not controlled with the addition of new or more intensive therapy, reduce by 1 dose level.b
 
If Grade 3 hypertension recurs despite dose reduction and antihypertensive therapy, reduce another dose level.c

4
 
Life-threatening consequences (e.g., malignant hypertension, transient or permanent neurologic deficit, hypertensive crisis)
	
Per institutional guidelines
	
Discontinue therapy

a. Patients requiring a delay of >4 weeks should go off protocol therapy

b. If BP remains controlled for at least one cycle, dose re-escalation permitted per investigator's discretion.

c. Patients requiring >2 dose reductions should go off protocol therapy.

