### **3.2 Exclusion Criteria**

- Previous assignment to treatment during this study. Subjects permanently withdrawn from study participation will not be allowed to re-enter study.
- Uncontrolled hypertension (systolic pressure  $\geq$ 140 mm Hg or diastolic pressure  $\geq$ 90 mm Hg on repeated measurement) despite optimal medical management.
- Active or clinically significant cardiac disease including:
  - Congestive heart failure – New York Heart Association (NYHA) > Class II.
  - Active coronary artery disease.
  - Cardiac arrhythmias requiring anti-arrhythmic therapy other than beta blockers or digoxin.
  - Unstable angina (angina symptoms at rest), new-onset angina within 3 months before randomization, or myocardial infarction within 6 months before randomization.
- Evidence or history of bleeding diathesis or coagulopathy.
- Any hemorrhage or bleeding event  $\geq$  Grade 3 within 4 weeks prior to prior to registration.
- Patients with thrombotic, embolic, venous, or arterial events, such as cerebrovascular accident (including transient ischemic attacks) deep vein thrombosis or pulmonary embolism within 6 months of the study registration.
- Previous exposure to VEGF inhibitor(s),
- Patients with any previously untreated or concurrent cancer that is distinct in primary site or histology from biliary tract cancer except cervical cancer in-situ, treated basal cell carcinoma, or superficial bladder tumor. Patients surviving a cancer that was curatively treated and without evidence of disease for more than 3 years prior to registration are

allowed. All cancer treatments must be completed at least 3 years prior to prior to registration).

- Patients with phaeochromocytoma.
- Known history of human immunodeficiency virus (HIV) infection or current chronic or active hepatitis B or C infection requiring treatment with antiviral therapy.
- Ongoing infection > Grade 2.
- Symptomatic metastatic brain or meningeal tumors.
- Presence of a non-healing wound, non-healing ulcer, or bone fracture.
- Renal failure requiring hemo- or peritoneal dialysis.
- Dehydration Grade  $\geq 1$
- Patients with seizure disorder requiring medication.
- Proteinuria  $\geq$  Grade 3 ( $> 3.5$  g/24 hours, measured by urine protein: creatinine ratio on a random urine sample).
- Active signs and symptoms of interstitial lung disease pleural effusion or ascites that causes respiratory compromise ( $\geq$ Grade 2 dyspnea).
- History of organ allograft (including corneal transplant).

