### 5. DOSING DELAYS/DOSE MODIFICATIONS

Doses will be delayed or reduced for clinically significant hematologic and non-hematologic toxicities that are related to protocol therapy according to the guidelines shown in the Dose Delays/Dose Modifications table that follows. Dose modifications will follow predefined dose levels. Dose adjustments for hematologic toxicity are based on the blood counts obtained in preparation for the day of treatment.

Modifications of regorafenib will follow the following predefined dose levels:		
#Dose level +1	160 mg, daily, orally	Four 40-mg tablets of regorafenib
Dose level 0 (Standard starting dose)	120 mg, daily, orally	Three 40-mg tablets of regorafenib
Dose level -1	80 mg, daily, orally	Two 40-mg tablets of regorafenib
Dose level -2	40 mg, daily, orally	One 40-mg tablet of regorafenib

#Only for those patients with no regorafenib dose related toxicity after the 1st cycle dose level of regorafenib 120mg/day, the dose level may escalate to 160mg/day for the second and subsequent

cycles.

If a patient experiences more than one toxicity, dose reduction should be according to the toxicity with the highest grade.

In the case of two or more toxicities of the same grade, the investigator may dose reduce according to that deemed most causally related to study treatment.

The following tables outline dose adjustments for toxicities related to study drug except hand-foot skin reaction, hypertension, and liver function test abnormalities.

**Table 5-1: Recommended dose modification for toxicities except hand-foot-skin reaction, hypertension and ALT/ST/bilirubin**

NCI-CTCAE v4.0 a	Dose Interruption	Dose Modification b	Dose for Subsequent Cycles
Grade 0-2	Treat on time	No change	No change
Grade 3	Delay until $\leq$ Grade 2 c,d	Reduce by 1 dose level	If toxicity remains $<$ Grade 2, dose re-escalation can be considered at the discretion of the treating (Sub-) investigator. If dose is re-escalated and toxicity ( $\geq$ Grade 3) recurs, institute permanent dose reduction.
Grade 4	Delay until $\leq$ Grade 2 c	Reduce by 2 dose levels. Permanent discontinuation can be considered at the treating (Sub-)investigator's discretion.	

a. NCI-CTCAE = National Cancer Institute - Common Terminology Criteria for Adverse Events, version 4.0

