**Table 5-5: Dose modifications/interruption for ALT and/or AST and/or bilirubin increases related to study drug**

Observed elevations	1 st Occurrence	Restart	Re-occurrence
AST and/or ALT $\leq$ 5 X ULN (< G3)	Continue dosing, with weekly monitoring of liver function until		

	transaminases return to <3 X ULN ( $\leq$ G1) or baseline.		
ALT and/or AST >5 X ULN ( $\geq$ G3)	Interrupt dosing, with weekly monitoring until transaminases return to < 3 X ULN or baseline.	If the potential benefit for reinitiating regorafenib is considered to outweigh the risk of hepatotoxicity: Reduce one dose level and measure serum liver tests weekly for at least 4 weeks.	Discontinue
ALT and/or AST > 20 X ULN ( $\geq$ G4)	Discontinue		
ALT and/or AST > 3 X ULN ( $\geq$ G2) with concurrent bilirubin > 2 X ULN	Discontinue treatment and measure serum liver tests weekly until resolution. Exception: patients with Gilbert's syndrome who develop elevated transaminases should be managed as per the recommendations outlined above for ALT/AST elevations.		
During the first 2 cycles of treatment, ALT, AST and bilirubin must be monitored weekly.			

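### Table 5-4: a Grade 3 hold can start on systolic pressure alone but ends on diastolic pressure alone, so some patients may restart while still Grade 3

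*Combined protocol and SAP*

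**What the plan says.** Table 5-4 defines Grade 3 hypertension by any one of three conditions: systolic ≥160 mmHg, diastolic ≥100 mmHg, or a need for more than one drug or for more intensive therapy than before. The antihypertensive aim in that row is diastolic ≤90 mmHg. The dosing column reads "Hold regorafenib until diastolic BP" is ≤90 mmHg and, for symptomatic patients, until symptoms have gone. It continues: "When regorafenib is restarted, continue at the same dose level". If pressure stays uncontrolled after new or stronger therapy, the dose drops one level, and by another level if Grade 3 recurs. Footnote a adds: "Patients requiring a delay of >4 weeks should go off protocol therapy".

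The text of Section 5.1 leaves hypertension management to local standards and the investigator's usual practice, asks that pressure be controlled medically where possible, and describes the table's dose reductions as suggested. It requires site blood pressure checks at least weekly for the first 8 weeks.

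The general rule in Table 5-1, which delays Grade 3 toxicities until they are Grade 2 or lower, does not apply here. Section 5 introduces it with: "The following tables outline dose adjustments for toxicities related to study drug except hand-foot skin reaction, hypertension, and liver function test abnormalities".

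**The concern.** A hold rule should end when the condition that started it has improved. Here systolic pressure can start the hold but has no part in ending it. An asymptomatic patient with isolated systolic hypertension in the Grade 3 range, and diastolic already ≤90 mmHg, satisfies the restart condition when the hold is ordered. As written, that patient may go back on the same dose with the triggering pressure unchanged.

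What is at stake is patient safety. Section 5.1 itself calls hypertension a known adverse event of regorafenib. For this subgroup, the protocol's protection during Grade 3 hypertension depends on the clinician doing more than the table asks. No efficacy analysis is involved.

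**Working it through.** There is no plan figure to reproduce. The check applies the written rule to specific readings.

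**Inputs** (Table 5-4, Grade 3 row)
- Grade 3 by pressure: systolic ≥160 or diastolic ≥100 mmHg.
- Current release: diastolic ≤90 mmHg, and symptoms resolved if there were any.
- Option A: current release and systolic <160 mmHg, the table's own boundary between Grades 2 and 3.
- Option B: current release and systolic <140 mmHg, the level used in Sections 3.2 and 5.1.

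Neither systolic release value is in the documents; both are proposals built from thresholds the protocol uses elsewhere.

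| Reading (mmHg) | Symptoms | Grade 3 by pressure? | Current | Option A | Option B |
|---|---|---|---|---|---|
| 175/82 | no | yes (systolic) | release | hold | hold |
| 160/90 | no | yes (systolic) | release | hold | hold |
| 165/95 | no | yes (systolic) | hold | hold | hold |
| 165/85 | yes | yes (systolic) | hold | hold | hold |
| 150/104 | no | yes (diastolic) | hold | hold | hold |
| 158/82 after treatment | no | no | release | release | hold |
| 138/82 after treatment | no | no | release | release | release |

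Of the five Grade 3 readings, the current rule releases two while they are still Grade 3. Either added condition brings this to none. The two options differ only for a patient such as 158/82, who is back in the Grade 2 range.

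There is also a delayed route to the same result. A patient at 165/105 is properly held at first. If diastolic falls to 90 while systolic stays at 165, the written rule releases that patient while still Grade 3. Both options close this route.

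**Does another part of the protocol supply a systolic release value?**
- Table 5-1 excludes hypertension, so its delay rule cannot be borrowed.
- The footnotes to Table 5-4 and the text of Section 5.1 give none.
- The protocol does use systolic limits elsewhere. Section 3.2 excludes patients with systolic ≥140 or diastolic ≥90 "mm Hg on repeated measurement) despite optimal medical management". Section 5.1 sets a call-in rule for outside readings of systolic ≥140 or ≥90 "mmHg diastolic then the subject must contact study personnel". The omission is therefore not explained by a protocol-wide reliance on diastolic pressure.

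**How do the other holds in Section 5 end?** Hand-foot skin reaction: "interrupt therapy for a minimum of 7 days, until toxicity resolves to Grade 0-1". Liver enzymes: "Interrupt dosing, with weekly monitoring until transaminases return to" <3 × ULN or baseline. Each ends on the measure that started it.

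**The case against.** The strongest reply is that the table is guidance under Section 5.1, which puts hypertension in the hands of the investigator and local standards. The Grade 3 row also does more than hold the drug: it calls for antihypertensives to be started, increased or added, and then for dose reduction if control fails. A patient restarted at 175/82 in the first 8 weeks would be re-measured within a week and could have the dose reduced. Diastolic-only aims and release conditions also appear in the Grade 2 row, which suggests a deliberate convention.

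Much of this stands as mitigation. The row as a whole is not inert for these patients, and a careful clinician would probably keep the drug off. But none of these provisions says when a hold may end. The table does not define control, and its only stated target is diastolic ≤90 mmHg, which this patient already meets. Section 5.1 attaches the word for optional to the dose reductions, whereas the hold is written as an instruction. The Grade 2 row is a different case: asymptomatic patients continue treatment there, and its hold also requires symptoms to resolve.

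Two further points are fair. The five readings were chosen to test the rule, so two of five is not a frequency. They also cover only the pressure triggers. An asymptomatic patient at 150/85 who is Grade 3 because a second drug is needed would be released at once under both the current rule and Option A; only Option B would hold that patient. Option A corrects the systolic trigger and leaves the therapy trigger as it is. Finally, adding a systolic aim at Grade 3 only would leave the Grade 2 aim diastolic-only, a minor unevenness.

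**Conclusion.** The concern holds. For asymptomatic patients with systolic ≥160 and diastolic ≤90 mmHg, the written release condition is met while the toxicity is still Grade 3, so the hold itself does nothing. Patients with symptoms, or with diastolic still above 90 mmHg, remain on hold.

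The number affected cannot be derived. The documents give no rate of isolated systolic Grade 3 hypertension. The Grade ≥3 drug-related hypertension rates in Section 2.2.2 (7% in the colorectal trial and 23% in the GIST trial) come from 160 mg dosing in other tumours and do not separate systolic from diastolic elevation. This trial starts at 120 mg and permits escalation to 160 mg.

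The conclusion rests on reading the table as written. It does not need an assumption about frequency. It is a safety wording fault that should be fixed; the primary endpoint, sample size, alpha and analysis are untouched.

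**What to change.** In the Grade 3 row of Table 5-4, make the hold end only when diastolic is ≤90 mmHg **and** systolic is <160 mmHg, keeping the symptom condition. Add the same systolic value to that row's treatment aim. At <160 mmHg the patient is no longer Grade 3 by pressure, and the Grade 2 row already lets asymptomatic patients continue. This also parallels the approach of Table 5-1, although that table does not govern hypertension.

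A stricter choice is systolic <140 mmHg, matching Sections 3.2 and 5.1. The investigator should choose between the two and state the value. The Grade 2 hold rule needs no change.

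The cost is a wording change in one row. No new measurement is needed, because each blood pressure reading already includes the systolic value. Some holds will last longer, and a few more patients may reach the 4-week limit in footnote a and leave protocol therapy. This is more likely with <140 than with <160 mmHg.

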## 5.2 Liver Function Abnormalities

For patients with observed worsening of serum liver tests considered related to regorafenib (i.e., where no alternative cause is evident, such as post-hepatitis cholestasis or disease progression), the dose modification and monitoring advice in Table 5-5 should be followed.

Regorafenib is a UGT1A1 inhibitor. Mild, indirect (unconjugated) hyperbilirubinemia may occur in patients with Gilbert's syndrome.

**Table 5-5: Dose modifications/interruption for ALT and/or AST and/or bilirubin increases related to study drug**

Observed elevations	1 st Occurrence	Restart	Re-occurrence
AST and/or ALT $\leq$ 5 X ULN (< G3)	Continue dosing, with weekly monitoring of liver function until		

	transaminases return to <3 X ULN ( $\leq$ G1) or baseline.		
ALT and/or AST >5 X ULN ( $\geq$ G3)	Interrupt dosing, with weekly monitoring until transaminases return to < 3 X ULN or baseline.	If the potential benefit for reinitiating regorafenib is considered to outweigh the risk of hepatotoxicity: Reduce one dose level and measure serum liver tests weekly for at least 4 weeks.	Discontinue
ALT and/or AST > 20 X ULN ( $\geq$ G4)	Discontinue		
ALT and/or AST > 3 X ULN ( $\geq$ G2) with concurrent bilirubin > 2 X ULN	Discontinue treatment and measure serum liver tests weekly until resolution. Exception: patients with Gilbert's syndrome who develop elevated transaminases should be managed as per the recommendations outlined above for ALT/AST elevations.		
During the first 2 cycles of treatment, ALT, AST and bilirubin must be monitored weekly.			

### 5.3 Prevention/management strategies for diarrhea

Diarrhea can be a common side effect of regorafenib. The same dose-modification algorithm used for skin toxicities can be used to address these toxicities. However, the preventive/management strategies for diarrhea should be consistent with local standards (e.g., anti-diarrheas and optimized hydration status).

Anti-diarrhea medications may be introduced if symptoms occur. Previous trials have shown that the diarrhea caused by TK inhibitors (e.g. sunitinib, sorafenib) could be managed with loperamide. The recommended dose of loperamide is 4 mg at first onset, followed by 2 mg every 2 to 4 hours until diarrhea-free for 12 hours.

